2.1 Working with Others: Developing Networks

Description

This session will increase your knowledge in the importance of developing networks and how your role as a registered practitioner can impact on patient care and the service which you provide. Multi-professional working and learning is essential for any healthcare practitioner. Networking gives you the opportunity to not only work alongside colleagues and other professionals, but also to understand different perspectives in care delivery (including patients and carers)

Learning Objectives

This session will support you to:

- Identify opportunities where working with patients and colleagues in the clinical setting can bring added benefits
- Create opportunities to bring individuals and groups together to achieve goals
- Promote the sharing of information and resources
- Actively seek the views of others

Module 2. Session 2

2.2 Working with Others: Building and Maintaining Relationships

Description

The aim of this session is to enhance your knowledge and appreciation of the importance of building and maintaining relationships as a newly qualified, or new to role healthcare professional, including the positive impact relationships can have on the quality of patient care and safety.

Learning Objectives

This session will support you to:

- Listen to others and recognize different perspectives
- Empathize and take into account the needs and feelings of others
- Communicate effectively with individuals and groups, and act as a positive role model
- Gain and maintain the trust and support of colleagues

Module 2. Session 3

2.3 Working with Others: Encouraging Contribution

Description

This session will discuss creating an environment where others have the opportunity to contribute and how you might encourage others to contribute from various backgrounds. We will also investigate the hurdles which you may encounter when encouraging contribution.

Learning Objectives

This session will support you to:

- Provide encouragement, and the opportunity for people to engage in decision making and to challenge constructively
- Respect, value and acknowledge the roles, contributions and expertise of others
- Employ strategies to manage conflict of interests and differences of opinion
- Keep the focus of contribution on delivering and improving services to patients

Module 2. Session 4.

2.4 Working with Others: Working within Teams

Description

This session will support you in your team to deliver and improve services.

Learning Objectives

This session will support you to:

- Have a clear sense of your role, responsibilities and purpose within the team
- Adopt a team approach, acknowledging and appreciating efforts, contributions and compromises
- Recognise the common purpose of the team and respect team decisions
- Lead a team, involving the right people at the right time

Module 3. Session 1.

3.1 Managing Services: Planning

Description

This session will enable you to contribute to the planning aspects of managing services. It will highlight who is involved, where you are in the process and what you can do to make a difference to your patient care.

Learning Objectives

This session will support you to:

- Identify the local strategy for the wider healthcare system and where your involvement supports plans for clinical services
- Gather feedback from patients, service users and colleagues to help develop plans
- Contribute their expertise to organizational planning processes
- Appraise options for planning services in terms of the benefits and risks

Module 3. Session 2

3.2 Managing Services: Managing Resources

Description

This session will help you to understand what resources are available and how to use your influence to ensure that they are used efficiently and safely whilst reflecting the diversity of needs.

Learning Objectives

This session will support you to:

- Accurately identify the appropriate type and level of resources required to deliver safe and effective services
- Ensure services are delivered within allocated resources
- Minimize waste
- Take action when resources are not being used efficiently and effectively

Module 3. Session 3

3.3 Managing Services: Managing People

Description

This session will give an overview of processes involved in managing people to enable you to provide direction, review performance, motivate others and promote equality and diversity.

Learning Objectives

This session will support you to:

- Provide guidance and direction for others using the skills of team members effectively
- Review the performance of the team members to ensure that planned service outcomes are met
- Support team members to develop their roles and responsibilities
- Support others to provide good patient care and better services

Module 3. Session 4

3.4 Managing Services: Managing Performance

Description

This session will discuss why measuring performance is a key part of delivering high quality, effective and safe services. It will help you consider how to improve performance and give some ideas for how to take this forward.

Learning Objectives

This session will support you to:

- Analyze information from a range of sources about performance
- Take action to improve performance
- Take responsibility for tackling difficult issues
- Build learning from experience into future plans

Module 4. Session 1

4.1 Improving Services: Ensuring Patient Safety

Description

This session will provide information about minimizing the risk to patient safety through deliverance of evidence based practice within the healthcare environment. It will discuss how this can improve the quality of care given to patients through root-cause analysis, risk assessment and will also consider how healthcare professionals can reflect on lessons learnt following patient safety incidents.

Learning Objectives

This session will support you to:

- Identify and quantify the risk to patients using information from a range of sources
- Use evidence, both positive and negative, to identify options
- Use systematic ways of assessing and minimizing risk
- Monitor the effects and outcomes of change

Module 4. Session 2.

4.2 Improving Services: Critically Evaluating

Description

This session will encourage you to think analytically and conceptually and to identify where services can be improved, working individually or as part of a team.

Learning Objectives

This session will support you to:

- Obtain and act on patient, carer and user feedback and experiences
- Assess and analyse processes using up-to-date improvement methodologies
- Identify healthcare improvements and create solutions through collaborative working
- Appraise options, plan and take action to implement and evaluate improvements
- Critical Evaluation

Module 4. Session 3

4.3 Improving Services: Encouraging Improvement and Innovation

Description

This session will explore ways to support the creation of a climate of continuous service improvement.

Learning Objectives

This session will support you to:

- Question the status quo
- Act as a positive role model for innovation
- Encourage dialogue and debate with a wide range of people
- Develop creative solutions to transform services and care

Module 4. Session 4

4.4 Improving Services: Facilitating Transformation

Description

This session will look at actively contributing to change processes that lead to improving healthcare.

Learning Objectives

This session will support you to:

- Model the expected change
- Articulate the need for change and its impact on people and services
- Promote changes leading to systems redesign
- Motivate and focus a group to accomplish change

Module 5. Session 1.

5.1 Setting Direction: Identifying the Contexts for Change

Description

This session will help you explore how to be aware of the range of factors to be taken into account when identifying the contexts for change.

Learning Objectives

This session will support you to:

- Demonstrate awareness of the political, social, technical, economic, organizational and professional environment
- Understand and interpret relevant legislation and accountability frameworks
- Anticipate and prepare for the future by scanning for ideas, best practice and emerging trends that will have an impact on health outcomes
- Develop and communicate aspirations

Module 5. Session 2.

5.2 Setting Direction: Applying Knowledge and Evidence

Description

This session will support you in gathering information to produce an evidence-based challenge to systems and processes, in order to identify opportunities for service improvements.

Learning Objectives

This session will support you to:

- Use appropriate methods to gather data and information
- Carry out analysis against an evidence based criteria set
- Use information to challenge existing practices and processes
- Influence others to use knowledge and evidence to achieve best practice

Module 5. Session 3

5.3 Setting Direction: Making Decisions

Description

This session will explore how to use your professional values, and the evidence to make good decisions.

Learning Objectives

This session will support you to:

- Participate in and contribute to organizational decision making processes
- Act in a manner consistent with the values and priorities of your organization and profession
- Educate and inform key people who influence and make decisions
- Contribute a clinical perspective to team, department, system and organizational decisions

Module 5. Session 4.

5.4 Setting Direction: Evaluating Impact

Description

This session will explore how outcomes are measured and evaluated in practice, how to take corrective action where necessary and how to justify your decisions

Learning Objectives

This session will support you to:

- Test and evaluate new service options
- Standardize and promote new approaches
- Overcome barriers to implementation
- Formally and informally disseminate good practice

Appendix 3: Questionnaire: English Version

I	D						
---	---	--	--	--	--	--	--

D	D	M	M	Y	Y
---	---	---	---	---	---

Self-Administered Survey Questionnaire

Instructions:

The questionnaire consists of 30 questions. Please, check or circle the appropriate answer. You should check it by circling the bullet sign before an appropriate answer.

Demographics Data:

1) My gender is

A. Male

B. Female

2) My date of birth is _____ (dd/mm/yy)

Patient's self-care: (Please rate the level of your agreement with each of the statements below choosing the numbers on the line)

3) My health is important to me

Strongly Disagree Strongly Agree

(1) (2) (3) (4) (5) (6) (7) (8) (9)

4) I lead a healthy lifestyle

Strongly Disagree Strongly Agree

(1) (2) (3) (4) (5) (6) (7) (8) (9)

5) I understand my health needs

Strongly Disagree Strongly Agree

(1) (2) (3) (4) (5) (6) (7) (8) (9)

6) I share responsibility for my health care

Strongly Disagree Strongly Agree

(1) (2) (3) (4) (5) (6) (7) (8) (9)

[figure not shown]
7) I respect my doctor's advice

Strongly Disagree Strongly Agree

[figure not shown]
(1) (2) (3) (4) (5) (6) (7) (8) (9)

Doctor self-cares: (Please rate the level of your agreement with each of the statements below choosing the numbers on the line)

[figure not shown]
8) My doctor appears calm

[figure not shown]
9) My doctor seems to look after her or his needs

[figure not shown]
10) My doctor looks healthy

11) My doctor demonstrates healthy behavior

[figure not shown]

12) My doctor appears happy

[figure not shown]

Patient cares about the doctor: (Please rate the level of your agreement with each of the statements below choosing the numbers on the line)

[figure not shown]
13) I am considerate of my doctor's needs

[figure not shown]
14) I have realistic expectations of my doctor

[figure not shown]
15) I advise my doctor on how to care for me

16) I show my doctor that I appreciate what she or he does for me

[figure not shown]

17) I understand when my doctor runs late

[figure not shown]

Patient empathy for the doctor: (Please rate the level of your agreement with each of the statements below choosing the numbers on the line)

[figure not shown]
18) I see my doctor as a person

[figure not shown]
19) I try to imagine myself in my doctor's situation

[figure not shown]
20) I try to see things from my doctor's perspective

21) I see my doctor in myself

[figure not shown]

22) I identify with my doctor by caring about myself

[figure not shown]

Doctor cares about the patient: (Please rate the level of your agreement with each of the statements below choosing the numbers on the line)

[figure not shown]
23) My doctor cares about me as a person

[figure not shown]
24) My doctor is an effective doctor

[figure not shown]
25) My doctor gives me the time I need

26) My doctor helps me understand my problem or illness

27) My doctor shares decision-making with me on how to manage my problem or illness

28) My current marital status is

- 1) Single
- 2) Married
- 3) Widowed
- 4) Divorce

29) On average my household expenditure per month is

- 1) Less than 50,000 drams
- 2) From 50,001 - 100,000 drams
- 3) From 100,001 - 200,000 drams
- 4) From 200,001 - 300,000 drams
- 5) Above 300,000 drams

30) My completed educational level is

- 1) Incomplete secondary (less than 10 years)
- 2) School (10 years)
- 3) Professional technical (10-13)
- 4) Institute/ University
- 5) Post-graduate

Appendix 4: Questionnaire: Armenian Version

I	D						
---	---	--	--	--	--	--	--

D	D	M	M	Y	Y
---	---	---	---	---	---

Ինքնուրույն լրացնելու համար նախատեսված հարցաշար

Ցուցումներ:

Հարցաթերթը բաղկացած է 30 հարցերից: Ընտրեք համապատասխան պատասխանը՝ շրջանի մեջ առնելով այն:

Անձնական տվյալներ:

1) Իմ սեռ՝

1. Արական

2. Իգական

[figure not shown]
2) Իմ ծննդյան ամսաթիվը _____ (օր/ամիս/տարի)

Որքանով է հիվանդը հետևում իր առողջությանը:

(Խնդրում ենք գնահատեք ձեր համաձայնության աստիճանը ստորև նշված արտահայտությունների հետ՝ նշելով գծի վրայի թվերը)

1) Իմ առողջությունը կարևոր է ինձ համար

[figure not shown]
Ամեննին
համաձայն չեմ

Լիովին
համաձայն եմ

2) Ես առողջ կենսակերպ եմ վարում

[figure not shown]
Ամեննին
համաձայն չեմ

Լիովին
համաձայն եմ

3) Ես գիտակցում եմ իմ առողջական կարիքները

[figure not shown]
Ամեննին
համաձայն չեմ

Լիովին
համաձայն եմ

4) Ես կիսում եմ պատասխանատվությունը իմ առողջության համար

[figure not shown]
Ամեննին
համաձայն չեմ

Լիովին
համաձայն եմ

5) Ես հարգում եմ բժշկիս խորհուրդը

Ամեննին
համաձայն չեմ

[figure not shown]

Լիովին
համաձայն եմ

[figure not shown]
Որքանով է բժիշկը հետևում իր առողջությանը:

(Խնդրում ենք գնահատել ձեր համաձայնության աստիճանը ստորև նշված արտահայտությունների հետ՝ նշելով զծի վրայի թվերը)

[figure not shown]
6) Բժիշկս հանդարտ տեսք ունի

[figure not shown]
7) Բժիշկս հետևողական է իր կարիքների նկատմամբ

[figure not shown]
8) Բժիշկս առողջ տեսք ունի

9) Բժիշկս առողջ վարվելակերպ է ցուցաբերում

10) Բժիշկս երջանիկ տեսք ունի

[figure not shown]
Որքանով է հիվանդը հոգատար բժշկի նկատմամբ:

(Խնդրում ենք գնահատելք ձեր համաձայնության աստիճանը ստորև նշված արտահայտությունների հետ՝ նշելով գծի վրայի թվերը)

11) Ես հաշվի եմ առնում բժշկի կարիքները

Ամեննին
համաձայն չեմ

[figure not shown]
Լիովին
համաձայն եմ

12) Ես իրատեսական ակնկալիքներ ունեմ բժշկիցս

Ամեննին
համաձայն չեմ

[figure not shown]
Լիովին
համաձայն եմ

13) Ես բժշկի խորհուրդներ եմ տալիս իմ խնամքի վերաբերյալ

Ամեննին
համաձայն չեմ

[figure not shown]
Լիովին
համաձայն եմ

14) Ես ցույց եմ տալիս բժշկիս, որ գնահատում եմ ինձ համար իր արածները

Ամեննին
համաձայն չեմ

[figure not shown]
Լիովին
համաձայն եմ

15) Ես հասկանում եմ, երբ բժիշկս ինչ-որ բանից ուշանում է

Ամեննին
համաձայն չեմ

Լիովին
համաձայն եմ

Որքանով է հիվանդը կարեկցում բժշկին:

(Խնդրում ենք գնահատելք ձեր համաձայնության աստիճանը ստորև նշված արտահայտությունների հետ՝ նշելով գծի վրայի թվերը)

16) Ես բժշկիս դիտարկում եմ որպես անձ	Ամեննին համաձայն չեմ ○-----○-----○-----○-----○-----○-----○-----○-----○ (1) (2) (3) (4) (5) (6) (7) (8) (9) Լիովին համաձայն եմ
17) Ես փորձում եմ ինձ բժշկիս կարգավիճակում պատկերացնել	Ամեննին համաձայն չեմ ○-----○-----○-----○-----○-----○-----○-----○-----○ (1) (2) (3) (4) (5) (6) (7) (8) (9) Լիովին համաձայն եմ
18) Ես փորձում եմ իրավիճակին նայել բժշկիս տեսանկյունից	Ամեննին համաձայն չեմ ○-----○-----○-----○-----○-----○-----○-----○-----○ (1) (2) (3) (4) (5) (6) (7) (8) (9) Լիովին համաձայն եմ
19) Ես իմ մեջ տեսնում եմ բժշկիս	Ամեննին համաձայն չեմ ○-----○-----○-----○-----○-----○-----○-----○-----○ (1) (2) (3) (4) (5) (6) (7) (8) (9) Լիովին համաձայն եմ
20) Իմ մասին հոգ տանելով ես ինձ բժշկիս հետ համախոհ եմ զգում	Ամեննին համաձայն չեմ ○-----○-----○-----○-----○-----○-----○-----○-----○ (1) (2) (3) (4) (5) (6) (7) (8) (9) Լիովին համաձայն եմ

Որքանով է բժիշկը հոգատար հիվանդի նկատմամբ:

(Խնդրում ենք գնահատելք ձեր համաձայնության աստիճանը ստորև նշված արտահայտությունների հետ՝ նշելով գծի վրայի թվերը)

21) Բժիշկս հոգ է տանում իմ մասին որպես անձ	
Ամեննին համաձայն չեմ
 
(1) (2) (3) (4) (5) (6) (7) (8) (9)
	
Լիովին համաձայն եմ

22) Բժիշկս շատ արդյունավետ բժիշկ է	
Ամեննին համաձայն չեմ
 
(1) (2) (3) (4) (5) (6) (7) (8) (9)
	
Լիովին համաձայն եմ

23) Բժիշկս ինձ հատկացնում է ինձ անհրաժեշտ ժամանակը	
Ամեննին համաձայն չեմ
 
(1) (2) (3) (4) (5) (6) (7) (8) (9)
	
Լիովին համաձայն եմ

24) Բժիշկս օգնում է ինձ հասկանալ իմ խնդիրը համ հիվանդությունը	
Ամեննին համաձայն չեմ
 
(1) (2) (3) (4) (5) (6) (7) (8) (9)
	
Լիովին համաձայն եմ

25) Բժիշկս խորհրդակցում է ինձ հետ իմ խնդրի կամ հիվանդության բուժման ընթացքի մասին	
Ամեննին համաձայն չեմ
 
(1) (2) (3) (4) (5) (6) (7) (8) (9)
	
Լիովին համաձայն եմ

26) Իմ ամուսնական կարգավիճակը՝

- 1) Չամուսնացած
- 2) Ամուսնացած
- 3) Այրի/ամուրի
- 4) Ամուսնալուծված

27) Իմ ընտանիքի միջին ամսական ծախսերը կազմում են՝

- 1) 50.000 դրամից պակաս
- 2) 50,001 - 100,000 դրամ
- 3) 100,001 - 200,000 դրամ
- 4) 200,001 - 300,000 դրամ
- 5) 300,000 դրամից ավել

28) Իմ կրթությունը՝

- 1) Թերի միջնակարգ (10 տարուց պակաս)
- 2) Միջնակարգ (10 տարի)
- 3) Մասնագիտական (ոչ բարձրագույն) կրթություն (10-13)
- 4) Բարձրագույն
- 5) Հետբուհական (գիտական աստիճան հետապնդող)

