3.3.3 Questionnaire

In order to measure the variables of interest for the evaluation, the study team proposes to use a self-administrated questionnaire (Appendixes 3 and 4). The questionnaire consists of validated questions to measure patient-physician relationship score from patients' perspective³³ and questions to measure socio-demographic characteristics of the survey participants.³⁷ The validated questionnaire to measure patient-physician relationship from patients' perspective is adopted from "patient measure of the doctor-patient caring" questionnaire by Buetow et al. (2011).³³ The self-administrated questionnaire for the

proposed project's evaluation consists of thirty questions. Among these thirty questions, twenty-five questions measure the patient-physician relationship score and five questions measure socio-demographic characteristics of the survey participants. In the questionnaire, the twenty-five questions measuring patient-physician relationship are grouped into five domains. Each domain consists of five questions.

The domains are as follows:

- 1) Patient's Self Care
- 2) Doctor's Self-care
- 3) Patient cares about the doctor
- 4) Patient empathy for the doctor
- 5) Doctor cares about the patient.

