Baseline Assessment (O₀) August 2015	
 a) Patients registered with Heratsi or Muratsan polyclinics b) Patients over the age of eighteen years old and under sixty five years old c) Patients visiting family physicians 	
Additional Criteria for the Follow-up Assessment (O₁) December 2015		
 a) Patients who registered with these polyclinics after August 2015 b) Patients who participated in the baseline assessment (O₀)
Additional Criteria for the Follow-up Assessment (O₂) June 2016		
 a) Patients who registered with these polyclinics after August 2015 b) Patients who participated in the baseline assessment (O₀) and the follow-up assessment (O₁)

Table 2: Variables and Sources of Data

Variables	Type	Measure	Sources
Dependent Variable Patient-Physician Relationship percent score	Numerical (Continuous)	Percent score (Minimum – 11% Maximum – 100%)	Self-administered questionnaire
Independent Variable Patients being from Intervention or Comparison polyclinics	Nominal (Dichotomous)	Patients of Family Physician from Heratsi or Muratsan	Self-administered questionnaire
Control Variables			
Age	Numeric (Continuous)	Age in Years	Self-administered questionnaire
Sex	Nominal (Dichotomous)	“Male” Or “Female.”	Self-administered questionnaire
Marital Status	Nominal	1) Single 2) Married 3) Widowed 4) Divorced	Self-administered questionnaire
Social-economic Status	Ordinal	1) Less than 50,000 drams 2) From 50,001 - 100,000 drams 3) From 100,001 - 200,000 drams 4) From 200,001 - 300,000 drams 5) Above 300,000 drams	Self-administered questionnaire
Educational Status	Ordinal	1) Incomplete secondary (less than 10 years) 2) School (10 years) 3) Professional technical (10-13) 4) Institute/University 5) Post-graduate	Self-administered questionnaire

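### The Armenian form departs from the English form and Table 2 in three places, chiefly a marital option 3 that overlaps option 1 and cannot be untangled after data collection

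*Protocol*

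**What the plan says.** The only outcome is the Patient-Physician Relationship percent score (Protocol, section 3.3.4 Variables). It is built from 25 items scored 1 to 9, with a raw range of 25 to 225 re-expressed as 11% to 100%. Section 3.3.3 Questionnaire states: "The questionnaire consists of validated questions to measure patient-physician relationship score from patients' perspective". That section also describes the translation. Two certified translators worked separately, the more suitable version was kept, native-speaking students reviewed it for content consistency, and a pretest in ten patients is still to come. Appendix 5 puts the pretest in July 2015 and the baseline assessment in August 2015. Section 3.3.2 Evaluation Study Design relies on an unchanged questionnaire at all three assessments.

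Marital status is one of five named control variables. Table 2 codes it as "1) Single 2) Married 3) Widowed 4) Divorced".

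The Armenian form restarts its numbering after the date of birth, so Armenian item *n* corresponds to English item *n* + 2. The places that differ are:

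- English "27) My doctor shares decision-making with me on how to manage my problem or illness" against Armenian "25) Բժիշկս խորհրդակցում է ինձ հետ իմ խնդրի կամ հիվանդության բուժման ընթացքի մասին".
- English "24) My doctor is an effective doctor" against Armenian "22) Բժիշկս շատ արդյունավետ բժիշկ է".
- Table 2 and English marital option 3, widowed, against Armenian option 3, *Այրի/ամուրի*. Armenian option 1 is "1) Չամուսնացած".

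**The concern.** A response option that overlaps another one is a data-capture fault. No later analysis can separate the patients who chose it. If some unmarried patients tick option 3, the data set codes them as widowed and the two kinds of patient are mixed in one level. Collapsing options 1 and 3 would remove the ambiguity only by giving up the distinction that Table 2 intends.

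This matters because the two polyclinics are not randomised. Section 3.3.2 Evaluation Study Design itself names selection bias as a threat and says that the groups might differ demographically. Adjustment for the five control variables is the planned answer to that, and a blurred control variable adjusts less completely.

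The two score items raise a lesser question. Both belong to the five-item domain on how the doctor cares for the patient. If their Armenian wording asks something stricter or somewhat different, those items record a slightly different quantity from the one that Appendix 3 describes.

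**Working it through.** **1. Side-by-side reading** (the English glosses of the Armenian are this review's own and should be confirmed by a native speaker).

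| Place | English form / Table 2 | Armenian form, in English | Difference |
|---|---|---|---|
| Marital option 1 | Single | Unmarried | None of substance |
| Marital option 3 | Widowed | Widowed / unmarried | Overlaps option 1 |
| English 24, Armenian 22 | Effective doctor | *Very* effective doctor (*շատ* added) | Stricter statement |
| English 27, Armenian 25 | Shares decision-making on managing the illness | Consults about the course of treatment | Consulting is weaker than sharing the decision |

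The Armenian words are coherent, so this is not damage from reading the PDF.

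**2. The plan's own figure.** 25 × 1 / 225 = 11.1% and 25 × 9 / 225 = 100%. The stated range reproduces, and the wording does not affect it.

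**3. Weight of the two items.** They are 2/25 = 8% of the score. One response level on one item is 100/225 = 0.44 percentage points. The planned change in section 3.3.3.1 Sample Size is 64.07 − 55.71 = 8.36 points.

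**4. Possible size of the marital effect.** The protocol gives no marital distribution and no score by marital status, so every input here is an assumption. Take a linear regression on group and reported marital status with no true group effect. The adjusted group difference is then a weighted average of the within-category differences, with weight n_A·n_B/(n_A + n_B) for each category. Only option 3 can contribute:

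bias = w₃ × (s_A − s_B) × (μ_single − μ_widowed)

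Here s is the share of single patients among those who tick option 3, and w₃ is the relative weight of that category.

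Assume 8% widowed and 5% divorced in both polyclinics, with single patients scoring below and widowed patients above married patients by the same amount. In absolute size:

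- *Lower case*: single 20% vs 30%, 25% of single patients tick option 3, scores 3 points either side (gap 6).
  - Shares: s = 0.05/0.13 = 0.385 and 0.075/0.155 = 0.484, difference 0.099.
  - Category weights: option 3 0.0707, option 1 0.0900, married 0.3080, divorced 0.0250. So w₃ = 0.0707/0.4937 = 0.143.
  - Bias = 0.143 × 0.099 × 6 = 0.085 points.
- *Upper case*: single 15% vs 35%, 50% tick option 3, scores 5 points either side (gap 10).
  - Shares: s = 0.075/0.155 = 0.484 and 0.175/0.255 = 0.686, difference 0.202.
  - Category weights: 0.0964, 0.0525, 0.3019, 0.0250. So w₃ = 0.0964/0.4758 = 0.203.
  - Bias = 0.203 × 0.202 × 10 = 0.41 points.
- *Less mis-ticking*: at 5% in the lower pattern the bias is 0.03 points. At 10% in the upper pattern it is 0.16 points.
- *Single and widowed patients score alike*: μ_single − μ_widowed = 0, so the bias is 0 at any mis-ticking rate.
- *Exclusive options*: option 3 holds only widowed patients, s = 0 in both polyclinics, and the bias is 0.

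The largest of these is 0.41/8.36 = 4.9% of the planned change.

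**The case against.** The strongest reply is that this is copy-editing. Option 1 comes first and fits an unmarried patient exactly, so few would choose an option that begins with widowed. A mis-ticking rate of 25% to 50% is therefore high. Score gaps of 3 to 5 points from married patients are 1.2 to 2 standard deviations on the protocol's SD of 2.5. The largest figures also need single and widowed patients to deviate in opposite directions. The planned model adjusts for age too, and adding it (assumed mean ages 28 for single and 57 for widowed patients) cuts the bias by about 20% to 30% at those mis-ticking rates. Two of the three measurable objectives are changes within the intervention polyclinic, where imbalance between polyclinics plays no part. The pretest might still catch the ambiguity. All of this stands, and it is why the effect is called small. It does not remove the overlap in the printed form.

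Two stronger readings are tempting and are not supported:

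- *The outcome is no longer the validated instrument.* A reader might infer this, but 23 of the 25 items are not in question. The protocol says that the questions were adopted from a published measure and does not claim a validated Armenian version. That measure is not in the documents, so only Armenian against English can be judged. Consulting a patient still concerns involvement in care, and *very* changes intensity rather than subject.
- *More patients are needed.* A reader might set 0.44 against 8.36 points and obtain 1/(1 − 0.053)² = 1.115, or 1.25 for both items. That assumes that the Armenian items register none of a one-level gain, which nothing in the documents shows. The printed sample-size formula also uses a difference of 0.585, not 8.36. At 8.36 points and SD 2.5 it would give (1.96 + 1.28)² × 12.5 / 8.36² = 1.9 per group, so that scaling has no bearing on a plan for 1,262.

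**Conclusion.** The point holds as a minor one. The Armenian marital options contradict Table 2 and overlap, and unmarried and widowed patients who tick option 3 cannot be told apart afterwards. Two of the 25 score items also differ from their English counterparts in intensity or content. With one form used at all assessments, and nothing to suggest that it differs between polyclinics, the item wording gives no reason to expect imbalance between the groups.

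The effect on the adjusted difference is probably small: 0 to 0.41 points over the assumptions shown, with the top of the range needing adverse choices throughout. The true value depends on marital distributions and score differences that are unknown. No stated figure, sample size or planned analysis changes.

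The conclusion rests on the glosses given above and on the Armenian form being the one that patients complete. The protocol does not say so outright, but this is the version to be pretested. If both languages were fielded, respondents would also be answering different questions under the same item.

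**What to change.** Before the July 2015 pretest, make three edits to Appendix 4:

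1. Change marital option 3 to *Այրի* only, in line with Table 2.
2. Delete *շատ* from item 22.
3. Reword item 25 to say that the doctor shares decisions with the patient on managing the problem or illness, in line with English item 27.

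Then use the corrected form unchanged at O₀, O₁ and O₂. The timing matters, because a correction after baseline would undercut the protocol's own argument that a constant questionnaire rules out an instrumentation threat. The cost is three wording changes on a form not yet pretested or fielded, plus notification of the IRB. No extra patients, staff or procedures are needed.
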